#### **Overall Design**

This study was originally designed as a 2-part (Phase IIb/III) study. However, given the decision to terminate recruitment, only Part A (Phase II) will be conducted.

This is a Phase II, global, randomized, parallel-group, double-blind, placebo-controlled, multicenter, proof-of-concept study to assess the safety and efficacy of 300  $\mu$ g and 600  $\mu$ g cotadutide compared with placebo, given once daily as an SC injection administered via a multidose pen, in adults with non-cirrhotic NASH with fibrosis stage F2 or F3.

The study will assess safety of cotadutide treatment. All efficacy endpoints are exploratory and include whether treatment with cotadutide results in a significant improvement compared to placebo in the proportion of participants with resolution of NASH without worsening of liver fibrosis at Week 48. Participants who are eligible according to the inclusion/exclusion criteria will be randomized in a 2:1:2:1 ratio to receive cotadutide 300  $\mu$ g, placebo matching cotadutide 300  $\mu$ g, cotadutide 600  $\mu$ g, or placebo matching cotadutide 600  $\mu$ g.

Participants will be  $\geq 18$  to  $\leq 75$  years of age (inclusive) with biopsy-proven NASH (historical biopsy performed  $\leq 180$  days from randomization or on-study biopsy) demonstrating a NAS  $\geq 4$  (with a score of at least 1 for each component: steatosis, lobular inflammation, and ballooning) and liver fibrosis stage F2 or F3. At randomization, participants will be stratified by the presence/absence of T2DM and by fibrosis stage. Each cotadutide treatment group will be placebo-matched with respect to titration schedule and dose levels. Participants will be screened in approximately 20 countries.

All liver biopsies will be read by a central pathology review committee.

An independent DMC will be established to monitor data on an ongoing basis to ensure safety

of participants enrolled in this study and to ensure the integrity of the study.

**Disclosure Statement**: This is a parallel group treatment study that is blinded to the participants and investigators. The study will include 4 treatment arms.

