### **Number of Participants:**

Approximately 600 participants will be screened/enrolled and approximately 55 are planned to be randomized to study intervention.

Note: "Enrolled" means a participant's, or their legally acceptable representative's, agreement to participate in a clinical study following completion of the informed consent process. Potential participants who are screened for the purpose of determining eligibility for the study but are not randomly assigned/assigned in the study, are considered "screen failures."

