#### **Data Monitoring Committee:** Yes

#### **Statistical Methods**

The primary analyses will be of safety, and analyses will be performed using the safety analysis set. Safety data will be presented using descriptive statistics unless otherwise specified and will not be formally tested. Safety events and findings will be summarized by treatment group. No formal hypothesis testing will be performed.

Exploratory efficacy analyses will use nominal 2-sided 5% significance levels (equivalent to nominal 1-sided 2.5% significance levels) unless otherwise stated.

The primary estimand of interest for the histological endpoints will use the treatment policy strategy. The treatment policy approach will apply to intercurrent events of treatment discontinuation, deviations from the protocol titration schedule, changes in background medication, liver events, or use of prohibited medication or other protocol deviations. The

treatment policy strategy will also be used to handle the intercurrent events for continuous endpoints.

[figure not shown]
Participants will be analyzed according to their randomized IP assignment and dose, irrespective of the treatment they actually received. Analyses will be performed using the FAS and/or per protocol analysis sets, as appropriate. The FAS will include all randomized and treated participants who received at least one dose of IP irrespective of their protocol adherence, addition or modification of background medications, discontinuation of study intervention or switches to alternative medications, and continued participation in the study.

For the exploratory analysis of binary histological endpoint(s) using FAS, participants with missing histology data due to any reason will be imputed as non-responders. The binary endpoint(s) will be analyzed using a Cochran-Mantel-Haenszel test with stratification by T2DM presence and F2/F3 fibrosis stages. The treatment effects will be summarized by the difference in proportions, 95% CI, and p-value.

In Part A, 300 participants were originally planned to be randomized to provide > 90% power for the test of each dose versus pooled placebo to detect a difference of 20% in NASH resolution assuming a placebo response rate of 15%. As a result of the decision to terminate recruitment, approximately 55 participants are planned to be randomized in the study.

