# 6.3 Measures to Minimize Bias: Randomization and Blinding

# **6.3.1 Method for Assigning Treatment Groups**

All participants will be centrally assigned to randomized study intervention using an IRT/RTSM. Before the study is initiated, the log-in information and directions for the IRT/RTSM will be provided to each site.

A participant is considered randomized into the study when the investigator notifies the IRT/RTSM that the participant meets eligibility criteria and the IRT/RTSM provides the assignment of blinded IP kit numbers to the participant.

In Part A, participants will be randomized 2:1:2:1 to receive cotadutide 300  $\mu$ g, placebo matching cotadutide 300  $\mu$ g, cotadutide 600  $\mu$ g, or placebo matching cotadutide 600  $\mu$ g. The randomization will be stratified by the presence/absence of T2DM and by fibrosis stage.

T2DM at the time of randomization is based on:

- Established diagnosis of T2DM OR
- HbA1c  $\geq$  6.5% (48 mmol/mol) by central laboratory assessment at Visit 1

Study intervention will be dispensed at the study visits summarized in Section 1.3.

Returned study intervention should not be re-dispensed to the participants.

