# 9.2 Sample Size Determination

Approximately 7440 participants were originally planned to be screened/enrolled to achieve 1860 randomly assigned to study intervention, including 300 in Part A. However, this study has prematurely stopped randomization as the cotadutide program has been discontinued. The sample size for this study includes approximately 55 randomized participants. The original

sample size calculations for Part A are detailed below.

In Part A, 300 participants were originally to be randomized in a 2:1:2:1 ratio. Approximately 100 participants were planned for each for each dose of cotadutide and 50 participants for each matching placebo group. This sample size was derived with respect to the comparison of each cotadutide group to the pooled placebo group for the proportion of participants with resolution of NASH without worsening of liver fibrosis at Week 48. The sample size would provide > 90% power for the test of each dose versus placebo to detect a difference of 20% in NASH resolution assuming a placebo response rate of 15%. The calculations assumed a 2-sided alpha level of 0.05.

The effects were assumed after any impacts from treatment discontinuation, early withdrawal, missing data imputation, etc. The assumed effect sizes for the histology-based endpoints took into account the PROXYMO interim analysis results as well as the published effects for a GLP-1 receptor agonist (Newsome et al 2021).

Note: "Enrolled" means a participant's, or their legally acceptable representative's, agreement to participate in a clinical study following completion of the informed consent process. Potential participants who are screened for the purpose of determining eligibility for the study but are not randomly assigned/assigned in the study, are considered "screen failures."

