General 17MAY2024		3.3.1.2 Analysis phase for listings of adverse events was defined.	Yes	Response to dry run findings

CATEGORY Change refers to:	Date	Description of change	In line with CSP?	Rationale
General	17MAY2024	3.3.2 A Week 52 analysis visit was specified for certain endpoints	Yes	Response to dry run findings
General	17MAY2024	4.1.2.2 Participants excluded from each analysis set will be listed with reason for exclusion	Yes	Clarification
General	17MAY2024	4.1.3.2 Only IPDs will be summarized and listed	Yes	Clarification
Efficacy Analysis 17MAY2024		4.2.3.1 Odds ratios will not be presented and unstratified estimator of difference in proportions will be used	Yes	Response to dry run findings
Efficacy Analysis 17MAY2024		4.2.3.2 Values of FAST used for analysis will be based on post-CDL calculations of FAST from values in the database.	Yes	Response to dry run findings
Efficacy Analysis 17MAY2024		4.2.3.3, 4.2.3.4 If models fail to converge or a collinearity issue is detected, models may be simplified.	Yes	Response to dry run findings
Efficacy Analysis 17MAY2024		4.2.3.4 Variables to be log- transformed prior to analysis were specified.	Yes	Response to dry run findings
Efficacy Analysis 17MAY2024		4.3 All measured concentration data for cotadutide participants will be summarized. Imputation for values LLOQ specified.	Yes	Response to dry run findings
Efficacy Analysis 17MAY2024		4.4 Definitions for ADA analyses were rephrased and reordered, but not fundamentally changed.	Yes	Align with standard tables
Safety Analysis 17MAY2024		4.5 All abnormal random glucose values will be considered as 'treatment emergent' in analysis since there is no planned random glucose value prior to randomization.	Yes	Response to dry run finding

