# 4.2.3.3 Handling of Dropouts and Missing Data

A post-baseline liver biopsy is planned for each participant at Week 48. Participants who discontinue study intervention early will have an early discontinuation visit. Participants will be encouraged to have the biopsy at Week 48 as planned in the CSP schedule of activities. Participants who are unwilling or unable to wait until Week 48 will have the biopsy procedure as part of the early discontinuation visit if they have received study intervention for at least 36 weeks. Participants who have not been on study intervention for at least 36 weeks will not have a biopsy at the early discontinuation visit.

Unless stated otherwise, the following rules will be used for missing data in exploratory endpoints:

- For biopsy endpoints analysis using the FAS analysis set, will impute missing observations as non-responders while analysis using the PP analysis set will exclude participants with missing data.
- Missing observations for ordinal endpoints will not be imputed, unless otherwise stated.
- Missing observations for continuous endpoints for analyses including multiple postbaseline timepoints will not be imputed.
- Missing observations for continuous endpoints for analyses including only a single post-baseline timepoint will be imputed using multiple imputation (monotone regression) separately by randomized treatment arm with stratification variables (baseline fibrosis stage and T2DM status) and baseline measurement for the endpoint as independent variables. If an issue is encountered for fitting an imputation model (eg, collinearity with intercept), a simplified imputation model may be used.

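### Read literally, by-arm imputation of single-timepoint Week 48 endpoints fits four coefficients in placebo arms of about nine; pooling placebo and naming the reduced model is a cheap precision gain

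*SAP*

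**What the plan says.** SAP 4.2.3.3 (Handling of Dropouts and Missing Data) separates two cases. Continuous endpoints analysed at several post-baseline timepoints are not imputed. Those with one post-baseline timepoint are imputed by "multiple imputation (monotone regression) separately by randomized treatment arm with stratification variables (baseline fibrosis stage and T2DM status) and baseline measurement" of the endpoint as predictors. The escape clause reads: "If an issue is encountered for fitting an imputation model (eg, collinearity with intercept), a simplified imputation model may be used". The SAP Amendment History describes the same change as: "If models fail to converge or a collinearity issue is detected, models may be simplified". No reduced model is named and no minimum df is given.

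The arms are set in the protocol. Section 1.1 states: "The study will include 4 treatment arms". Section 6.3.1 gives the ratio: "In Part A, participants will be randomized 2:1:2:1 to receive cotadutide" at 300 µg or 600 µg or the matching placebo of either dose. The synopsis says that "approximately 55 are planned to be randomized to study intervention".

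Pooled placebo appears only in the sample-size text. Protocol 9.2 bases the size on the "comparison of each cotadutide group to the pooled placebo group", and Protocol 1.1 (Statistical Methods) and SAP 1 repeat the idea. Neither SAP 4.2.3.3 nor 4.2.3.4 says that placebo is pooled, and 4.2.3.4 does not define the levels of the ANCOVA treatment term.

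**The concern.** With 50 participants per placebo arm, as planned for the 300-participant design, a 4-coefficient model per arm was harmless. With about 9 it is fragile. Regression imputation draws the residual variance from its posterior, and with few df that draw is large and unstable. The excess passes through Rubin's rules into the reported interval. A regression with 2 or 3 residual df runs without a collinearity or convergence message, so nothing in the SAP obliges anyone to simplify it. A programmer could read the sentence as four arms or as three groups and obtain different intervals. With about 55 participants, interval width is most of what the exploratory efficacy results can offer.

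**Working it through.** **The plan's own figure.** Power above 90% for 15% against 35%, 2-sided 0.05. With 100 per dose and 100 pooled placebo:

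Φ[(0.20 − 1.96·√(2·0.25·0.75/100)) / √(0.15·0.85/100 + 0.35·0.65/100)] = Φ(0.0800/0.0596) = 91.0%.

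Against a single placebo arm of 50 the same method gives 75.1%. So the stated power needs pooled placebo as the comparator.

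**Arm sizes and df.** 55 × (2, 1, 2, 1)/6 = 18.3, 9.2, 18.3, 9.2. Coefficients: intercept, baseline, T2DM, fibrosis stage = 4. Residual df in a 9-person arm = 9 − missing − 4, which is 5, 4, 3, 2 for 0, 1, 2, 3 missing. The drawn variance is inflated on average by df/(df − 2): 1.67, 2.0, 3.0, and no finite mean at df 2. For 18 pooled placebo participants with none missing, df is 14 and the factor is 1.17.

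**How often.** The documents give no missing rate; 10/20/30% is assumed. Binomial probability that at least one of the two placebo arms has:
- 2 or more missing (df 3 or less): 40/81/96%;
- 3 or more missing (df 2 or less): 10/46/79%.

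Pooled placebo needs 11 or more of 18 missing to reach df 3 or less: under 0.01%, 0.02% and 0.6%.

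**Which endpoints.** SAP Table 6 gives a Week 48 window of Days 2–378 to FibroScan, FAST, Agile 3+, BARD, lipids, ELF, Pro-C3, FIB-4, fasting glucose, C-peptide and adiponectin. Protocol Table 4 collects these, or their inputs, at the early-discontinuation visit, so such a value usually fills Week 48. Body weight differs. No SAP window table names it; Protocol Table 4 puts it in the abbreviated physical examination, and SAP Table 3 gives that examination Days 309–351. On that inference, an early-discontinuation weight before Day 309 does not count as Week 48. FibroScan endpoints stay exposed where the scan was not done.

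**Effect on the interval.** Simulation of percent weight change with assumed inputs: arms 18/9/18/9, true difference −6 points, SD 6, T2DM and F3 each 50%, data missing completely at random, 50 imputations (the SAP gives no number), 2,000 trials per rate. The ANCOVA pools placebo (assumed) and uses Rubin's rules. Median 95% half-width, 600 µg versus placebo, in percentage points (4.1 with nothing missing):

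| Imputation | 10% | 20% | 30% |
|---|---|---|---|
| Four arms, no fallback | 5.0 | 6.3 | 8.8 |
| Four arms, intercept-only below df 3 | 4.9 | 5.6 | 6.5 |
| Four arms, baseline-only below df 3 | 4.9 | 5.8 | 7.0 |
| Placebo pooled | 4.6 | 5.2 | 6.0 |

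Narrowing from pooling, no fallback: 1 − 4.6/5.0 = 8%, 1 − 5.2/6.3 = 17%, 1 − 6.0/8.8 = 32%. Repeat runs gave 6–8, 16–18 and 29–33%. Against the intercept-only rule it is 6/7/8%. In a separate run of 800 trials with 30 imputations, four arms with baseline-only below df 5 gave 4.7/5.4/6.6 against 4.6/5.2/6.1 pooled, which is 2/4/8%; a further run gave about 1/4/7%. A late trigger does less: against baseline-only below df 3 the gain is 6/10/14%.

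Coverage was 97/99/99% for four arms and 96/97/97% pooled. Without a fallback, some arm had no residual df in 0/3/14% of trials; these are left out of the half-widths. With unequal arms (SD 4 placebo and 8 active, different baseline slopes) half-widths were 5.5/6.8/8.6 for four arms, 5.5/6.3/6.9 with the intercept-only fallback and 5.3/6.0/6.7 pooled: gains of 4/12/22% without the fallback and 3–5% with it.

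**The case against.** The strongest case on the other side has four parts.

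- **The fallback exists and is open-ended.** Collinearity is only an example of a fitting issue, and a model with no residual df is plainly one. The clause was added after dry-run findings, so fitting problems had been considered. This stands: a reader might take 8/17/30% as the expected gain, but that figure assumes the clause is never used. It does not remove the point, because a fit with 2 or 3 df is not clearly an issue under the clause, use is discretionary, and the reduced model is unnamed.
- **Few endpoints are exposed.** A reader might infer that all Week 48 continuous endpoints are affected. The Table 6 window and the rule against imputing multi-timepoint endpoints (for example HbA1c, ALT, AST and SBP through Week 48) show otherwise. This stands.
- **Little may be missing.** SAP 4.2.3.4 counts off-treatment values at Week 48, and Protocol 7.1 encourages participants who stop treatment to attend remaining visits. At 5% missing, half-widths were 4.5 with four arms and 4.3 pooled. With nothing missing there is no effect.
- **By-arm imputation is valid.** It avoids assuming that the two placebo arms share slope and variance, and coverage is above nominal. A reader might infer bias or false positives; neither the documents nor the calculations support that.

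Pooling for imputation alone would also be incomplete, because a four-level treatment term in the ANCOVA would not match it.

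**Conclusion.** The point holds as a low-priority improvement. Taken at its word, the imputation sentence fits 4 coefficients in placebo arms of about 9, and no stated rule prevents fits on 2 or 3 df. The cost is precision, and occasionally a model that cannot be estimated, chiefly for percent change in body weight and for FibroScan-based endpoints where the scan was not done. Pooling placebo gains about 8/17/30% in interval width at 10/20/30% missing if no fallback is applied, and about 1–8% if a sensible reduced model is applied early enough. These sizes rest on assumed missing rates, data missing completely at random, a pooled-placebo ANCOVA and a body-weight window inferred from Table 3. The percentages do not depend on the assumed SD, since all half-widths scale with it. The endpoints are exploratory with nominal p-values.

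**What to change.** Before unblinding, make three edits to the SAP:

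1. In 4.2.3.3, impute separately by treatment group (cotadutide 300 µg, cotadutide 600 µg, pooled placebo) instead of by randomized arm.
2. In 4.2.3.4, define the ANCOVA treatment factor with the same three groups.
3. In 4.2.3.3, make the fallback a rule: name the reduced model (for example, baseline value only) and the minimum residual df below which it applies (for example, 5). The exact threshold is a choice; what matters is that it is stated. Once placebo is pooled this is a safety net: it triggered in 0/0.2/6% of simulated trials at 10/20/30% missing.

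The cost is a few sentences and a change of the BY variable in the imputation code. Protocol 9.4.2 asks only for multiple imputation, so pooling does not contradict it. The downside is that the two matching placebo arms are treated as exchangeable, as the pooled-placebo comparison already assumes. With their true means set 2 or 4 points apart, pooled imputation kept 97–98% coverage at 20–30% missing.
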